# 0. Abbreviations

**iFOBT** fecal occult blood test fecal immunochemical test FIT **IFU** instructions for use stool-derived eukaryotic RNA seRNA droplet digital polymerase chain reaction ddPCR CRC colorectal cancer AA advanced adenoma OA other precancerous adenomas food and drug administration FDA sessile serrated adenoma / polyp SSA tubular adenoma TA VA villous adenoma tubulovillous adenoma TVA **IRB** institutional review board sensitivity Sen specificity Sp standard operating procedure SOP informed consent form **ICF** 

# 1. Background and Rationale

# 1.1 Study Synopsis

Sponsor	Geneoscopy Inc. [name]
Primary Objectives	The primary objective of the ColoRectal Cancer and Pre-Cancerous Adenoma Non-InvasiVE Detection Test Study study (CRC-PREVENT) is to determine sensitivity for colorectal cancer, advanced adenomas, and specificity for other precancerous adenomas, hyperplastic polyps, other lesions, and no findings on a colonoscopy for Geneoscopy's multi-target stool RNA assay (mt-sRNA) using colonoscopy as the reference methods. Lesions will be confirmed by histopathologic examination.
Sites	Recruitment for this screening study will utilize a decentralized model. It is estimated that participants recruited for this study will be derived from all 48 contiguous United States and will visit over 6,000 different clinical sites for endoscopy procedures.
Population	Participants over the age of 45, who are at average-risk of developing colorectal neoplasms and are considered enrolled after understanding and consenting to the informed consent form (ICF).
Investigational Device	Geneoscopy's mt-sRNA Test
Primary endpoint	The co-primary endpoints for this study are sensitivity and specificity of the mt-sRNA test for colorectal cancer, advanced adenomas, other precancerous adenomas,

CEN	EOG	COD	Y, INC	
GEIV	EUS	CUP	I, IIV	

**Document Number: VAL-PRT-0041** 

	hyperplastic polyps, and no findings on a colonoscopy, with comparison to the colonoscopy result and histopathologic diagnosis of all lesions discovered during colonoscopy.
Study Procedures	This study will be a prospective analysis conducted by Geneoscopy Inc. to evaluate the multi-target stool RNA test (mt-sRNA test) for colorectal neoplasia screening. Patients who are eligible for a colonoscopy (i.e., asymptomatic, average risk individuals over the age of 45 who are not up-to-date with screening guidelines) will be enrolled in the study. Stool sample collection kits will be sent to individuals who enroll in the study. The collection kit provides information on how to collect a stool swab using a fecal immunochemical test (FIT / iFOBT) and how to collect a stool sample. After a stool sample is produced, patients will swab the stool sample using the iFOBT Sampling Bottle according to instructions for use (IFU) and will return the stool sample via mail courier to Geneoscopy's Laboratories. After samples are sent to the labs, participants will be directed to receive a colonoscopy. If a lesion is removed during the colonoscopy, the participant's tissue sample will be sent for histopathology review. Histopathology is the review of the tissue by a pathologist to determine if the tissue is benign, premalignant, or malignant. The colonoscopy report, physician reports, and the histopathology report will be provided to Geneoscopy. Stool samples returned to Geneoscopy's Laboratories by the participant will be subjected to the mt-sRNA test system, which includes targeted nucleic acid enrichment and biomarkers quantification via droplet digital polymerase chain reaction (ddPCR). The iFOBT Sampling Bottle returned in the Collection Kit will also be read by laboratory technologists at Geneoscopy Inc. This study will be used for validation of the investigational device.
Study Duration	Once a participant is enrolled in the study, the subject will produce a stool sample. Participants will be requested to submit the within 120 days of colonoscopy completion. Subjects will not be evaluated after the colonoscopy procedure, however all reports associated with findings from the colonoscopy report will be collected. These reports will be centrally reviewed. Subjects may be contacted by the investigation site for up to five (5) years following completion of the study to gather additional information.

#### 1.2 Background Information

Colorectal cancer (CRC) is the third most common cancer in both men and women in the United States, the second deadliest cancer globally, and accounted for over 50,000 deaths in 2018 in the US alone.  Disease onset is typically insidious, starting as a small polyp which can take several years to further accrue somatic mutations and develop into an invasive carcinoma.  If detected early, CRC has a five-year survival rate of 92%. However, 63% of newly diagnosed patients have advanced disease, with an associated five-year survival rate as low as 14%.  Late-stage diagnosis typically results from patient noncompliance with screening guidelines, indicating that these cancers could have been detected earlier by following standard protocols. CRC screening compliance has remained stagnant over the past 20 years and is currently estimated to be approximately 60%,  which is well below the National Colorectal Cancer Roundtable's goal of 80%.  In addition, nearly a quarter of all adults in at-risk populations have never before been screened.  Historically, low compliance rates have been due to the inconvenience, unpleasantness, and perceived hazards of colonoscopies. In an open-ended survey of 660 patients regarding the most important

Title: CRC-PREVENT Clinical Validation Protocol

**Document Number: VAL-PRT-0041** 

barrier to CRC screening, three of the top four responses cited were directly related to the invasive nature of a colonoscopy: "afraid/fear," "prep unpleasant," and/or "anticipated pain". Therefore, it is likely that a noninvasive alternative screening method would significantly increase the number of patients opting for CRC screening.

While colonoscopies are currently the gold-standard for colorectal cancer screening, the procedure does have associated risk to the patient. A colonoscopy procedure can result in an adverse event, which includes: pain (2.59%), hemorrhage (0.28%), perforation (0.05%). These complications can lead to hospitalization (1.17%), urgent care visit (2.34%), or in rare cases death (0.01%). An additional risk to the patient is a false negative result. It has been described that colonoscopies can miss 15-24% of all adenomas, 6-11% of advanced adenomas, and 1% of carcinomas. Miss rates are associated with withdrawal time, quality of bowel preparation, colonoscopy techniques, and polyp characteristics. 14

While many noninvasive tests have been developed to address compliance issues, none compare to the diagnostic accuracy of a colonoscopy.  Currently, the most accurate noninvasive diagnostic (Cologuard, Exact Sciences) cites a CRC sensitivity of 92%.  However, the advanced adenoma (AA) detection rate for this test is only 42%.  Other noninvasive stool-based tests include the fecal occult blood test and the fecal immunochemical test (FIT), which use lateral flow for detection of blood in stool. These alternatives can be highly sensitive (79%) and specific (94%) for CRC, but have AA sensitivities of less than 30%.  Accurate detection of precancerous adenomas would allow for preemptive excision of dysplastic tissue prior to carcinogenesis, thus reducing CRC incidence and the associated morbidity and mortality. 

Detection of precancerous lesions, including advanced and non-advanced adenomas, is essential for cancer prevention. Precancerous adenomas are categorized by both size and pathology. Advanced adenomas and non-advanced adenomas include the following findings on a colonoscopy:

- $\geq$ 10 adenomas of any size, shape, or pathology classification
- adenoma with high-grade dysplasia
- adenoma with carcinoma in-situ
- adenoma with villous architecture
- adenoma with tubulovillous architecture
- tubular adenoma ≥ 10mm
- 5-10 tubular adenomas
- Sessile serrated adenoma / polyp ≥ 10mm
- 5-10 tubular or sessile serrated adenomas / polyp
- 1-2 tubular or sessile serrated adenoma / polyp between 5-10mm
- >20 hyperplastic polyps
- Hyperplastic polyp  $\ge 10$ mm
- 3-4 tubular or sessile serrated adenoma / polyp <10mm
- 1-2 tubular or sessile serrated adenoma / polyp ≤5mm

Malignant transformation rates and recommended screening intervals for each of the above lesions vary. Lesions with the most aggressive natural history include those with high-grade dysplasia or carcinoma *in*-

Title: CRC-PREVENT Clinical Validation Protocol

**Document Number: VAL-PRT-0041** 

situ with an annual malignant transformation rate of 50%. Other lesions with high acuity include those with tubulovillous or villous architecture with an annual malignant transformation rate of 30-50% and sessile serrated adenomas / polyps (2-3 crypts) with an annual malignant transformation rate of approximately 10%. The malignant transformation rate for other adenomas is between 0.25-5%. For patients with fewer than 20 small hyperplastic polyps or patients with no findings on a colonoscopy, the risk of development of a malignant lesion is unlikely.

Given the range of genomic variants that can lead to malignant transformation of healthy colonic tissue, genomic assays that target a small number of canonical variants are not sufficiently sensitive for precancerous lesions. However, colorectal cancer, advanced adenomas, and other precancerous adenomas can be detected by evaluating a panel of RNA biomarkers that encompass the broader effects of multiple pathological variants. While the analysis of human RNA biomarkers in stool samples has been extremely challenging due to extensive RNA degradation and a high bacterial transcript burden, Geneoscopy has developed a method to reliably extract and evaluate stool-derived eukaryotic RNA (seRNA) biomarkers. Using this extraction method, Geneoscopy has developed a multi-factor mt-sRNA test that combines 8 stool-derived eukaryotic RNA (seRNA) biomarkers, patient demographic information (smoking status), and a fecal immunochemical test (FIT / iFOBT) to sensitively detect colorectal cancer, advanced adenomas, and other precancerous adenomas.

Biomarker discovery for the mt-sRNA test was completed using a 264-patient cohort. In this study, 639 transcripts associated with malignancy were assessed for association with advanced adenomas and colorectal cancer. Using a 154-patient training set and a 110-patient testing set, a final cohort of seRNA biomarkers were identified for the molecular component of the mt-sRNA test. A subsequent feasibility study was conducted using a multi-center, prospective study design. For this clinical trial, 1,305 participants were recruited to participate using an online enrollment strategy. Participants received a collection kit in the mail, deposited a stool sample, and shipped the sample back to Geneoscopy's centralized lab. After processing the sample using the mt-sRNA test, participants were directed to receive a colonoscopy at their local endoscopy center. mt-sRNA test results were compared to the colonoscopy results to determine mt-sRNA test accuracy. The hold out testing set (n = 366 participants) demonstrated a 100% sensitivity for colorectal cancer (n = 2), a 60% sensitivity for advanced adenomas (n = 50), a 25%sensitivity for other precancerous adenomas (n = 139), 80% sensitivity for hyperplastic polyps (n = 74), and 85% sensitivity for no findings on a colonoscopy (n = 101). To improve confidence surrounding the cancer sensitivity, 20 samples were obtained retrospectively from patients with known diagnosis of colorectal cancer prior to surgical resection or therapy. The mt-sRNA test identified 19 of these 20 patients as positive (95% sensitivity).

The CRC-PREVENT clinical validation study described here will assess the clinical sensitivity and clinical specificity of the mt-sRNA test. A clinical research organization (CRO) will be involved with patient recruitment. This entity will direct patients through providing a stool sample to Geneoscopy and conducting a standard of care colonoscopy. This optical colonoscopy procedure will serve as the reference method for the mt-sRNA test. Lesions observed via colonoscopy will be confirmed by histopathology and classified based on findings listed in **Table 1**. Stool samples eligible for the clinical study will be collected and assessed in accordance with mt-sRNA test's predefined standard operating procedures and the test's composite score will be generated using the Analysis Software. The results from the colonoscopy and

GEN	FOS	COPY,	INC
OLIV	LUJ	COI I,	, IIIC.

**Document Number: VAL-PRT-0041** 

histopathology will be blinded to laboratory technologists at Geneoscopy. To assess the accuracy profile, colonoscopy results will be stored by a second clinical research organization (CRO). Ultimately, Geneoscopy study members will supply the CRO with mt-sRNA test results. Study members at the CRO will link mt-sRNA test results to colonoscopy results to assess the primary endpoints of this study.

Table 1. Histopathological category definitions

Category	Binary Category	Description
Colorectal Cancer (CRC)	Positive	Stage I-IV colorectal cancer, any size
Advanced Adenomas (AA)	Positive	High-grade dysplasia or ≥10 adenomas, any size Tubulovillous adenoma, any size Tubular adenoma, ≥10mm Traditional serrated adenoma, ≥10mm
Medium Risk Adenomas (MRA)	Negative	Hyperplastic polyp or SSL, ≥10mm 5-9 adenomas (TA + SSL), <10mm 3-4 adenomas (TA + SSL), <10mm
Low Risk Adenomas (LRA)	Negative	1-2 adenomas (TA + SSL), 5-9mm 1-2 adenomas (TA + SSL), <5mm
No Findings (NEG)	Negative	Hyperplastic polyps, <10mm Benign lesions, any size No lesions on colonoscopy

# 2. Objectives

#### 2.1 Primary and Secondary Objectives

The primary objective of this study is to determine the sensitivity and specificity of Geneoscopy's mt-sRNA test for colorectal neoplasias (i.e., colorectal cancer and advanced adenomas) using colonoscopy as the reference method. Lesion categories will be confirmed by histopathologic examination. Performance of the mt-sRNA test will be evaluated based on comparison of the mt-sRNA test result with the histopathological category (**Table 1**). The primary objectives will support clinical claims to be used in regulatory submissions. If acceptance criteria are met, findings pertaining to all primary and secondary objectives will be reported to the clinical community through academic presentations and in a peer-reviewed publication.

Four co-primary performance measures are specified as:

- mt-sRNA test sensitivity for subjects with colorectal cancer (CRC), which is the percentage of individuals with a diagnosis of colorectal cancer (**Table 1**) that were detected as positive by the mt-sRNA test.
- mt-sRNA test sensitivity for subjects with advanced adenomas (AA), which is the percentage of individuals with a diagnosis of advanced adenoma (**Table 1**) that were detected as positive by the mt-sRNA test.
- mt-sRNA test specificity for subjects with negative findings, which is the percentage of individuals with a diagnosis of benign polyps, or no findings on a colonoscopy (**Table 1**) that were detected as negative by the mt-sRNA test.

CENEOCCODY INC	Title: CRC-PREVENT Clinical Validation Protocol
GENEOSCOPY, INC.	Document Number: VAL-PRT-0041

There will also be three co-secondary performance measures:

- mt-sRNA test sensitivity for subjects with high-grade dysplasia, which is the percentage of individuals with a diagnosis of carcinoma *in situ* or advanced adenoma with high grade dysplasia (**Table 1**) that were detected as positive by the mt-sRNA test.
- mt-sRNA test sensitivity for subjects with villous / tubulovillous adenomas, which is the percentage of individuals with a diagnosis of advanced adenoma with villous or tubulovillous growth pattern, any size (Table 1) that were detected as positive by the mt-sRNA test.
- mt-sRNA test sensitivity for subjects with sessile serrated adenomas / polyps, which is the percentage of individuals with a diagnosis of hyperplastic polyps or sessile serrated adenoma / polyp (SSA) ≥ 10mm any size (Table 1) that were detected as positive by the mt-sRNA test.

For each of these metrics, the two-sided 95% exact binomial confidence intervals will be provided. Criteria for success for these metrics requires the following:

- With regards to the mt-sRNA test sensitivity for subjects with CRC, the sensitivity of CRC must be greater than 90% and the lower bound of the 95% two-sided confidence interval must be greater than 80%.
- With regards to the mt-sRNA test sensitivity for subjects with AA, the sensitivity of AA must be greater than 45% and the lower bound of the 95% two-sided confidence interval must be greater than 40%.
- With regards to the mt-sRNA test specificity for subjects with no findings on a colonoscopy, the specificity must be greater than 80%.

These will be considered as a joint hypothesis as follows:

```
H0: CRC_{Sen} \le 0.90 or AA_{Sen} \le 0.45 or Sp \le 0.80 H1: CRC_{Sen} > 0.65 and AA_{Sen} > 0.45 and Sp > 0.80
```

where CRCSen is the mt-sRNA test sensitivity for subjects with CRC, AASen is the mt-sRNA test sensitivity for subjects with AA and Sp is the specificity for no findings on a colonoscopy. The associated p-values for two-sided 0.05 exact binomial tests will also be provided.

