**Document Number: VAL-PRT-0041** 

# 3.5 Sample Size Requirements

The overall sample size is driven by the need to obtain enough CRC cases so that the lower 95% exact confidence limit for the sensitivity is at least 80%. Table 2 shows the smallest number of CRC cases that would meet this condition for each of 0 - 5 False Negatives.

Table 2. Cases to meet primary objective criteria

Number of CRC Cases	# False Negative	Observed Sensitivity	Lower 95% CL	Upper 95% CL
17	0	100.0%	80.5%	100.0%
26	1	96.2%	80.4%	99.9%
34	2	94.1%	80.3%	99.3%
41	3	92.7%	80.1%	98.5%
48	4	91.7%	80.0%	97.7%
55	5	90.9%	80.0%	97.0%

A sample size of 48 would allow up to 4 false negatives corresponding to an observed sensitivity of 91.7%. Assuming a prevalence of 0.6% in the intended use population, a starting sample size of 8,500 will have 68% chance of yielding at least 48 CRC cases. Given the low prevalence of CRC cases, a small difference between the actual prevalence and the postulated prevalence could lead to too few CRC cases.

The number of CRC cases will be tracked by unblinded study members at the CRO to determine when to stop enrollment. Enrollment will be arrested when a sufficient number of confirmed cases of colorectal cancer have been identified among the cohort to achieve study endpoints. To assess cessation of enrollment, an initial 8,500 participants will be recruited into the study. After this initial enrollment the number of confirmed CRC cases will be assessed against the required number of CRC cases by unblinded study members. If the total number of required cases have not been met after recruitment of 8,500 patients, additional participants will be recruited in 1,000-patient intervals. Enrollment will continue until all endpoints are fully powered.

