**Document Number: VAL-PRT-0041** 

Never smoked Previous smoker Currently smoke					
Sex Female Male No Answer	x (xx)				
Family History of CRC No Yes	x (xx)				
Ethnic Background American Indian / Alaska Native African American / Black Asian White Native Hawaiian / Pacific Islander Other Prefer not to answer	x (xx)				
Race Hispanic Non-Hispanic Other Prefer not to answer					
Average Income \$200,000 or More \$150,000-\$199,999 \$100,000-\$149,999 \$75,000-\$99,999 \$50,000-\$74,999 \$30,000-\$49,999 Under \$29,999 Prefer not to answer	x (xx)				
Insurance No Insurance Private Insurance Public Insurance (Medicaid) Public Insurance (Medicare Advantage) Public Insurance (Medicare) Self-Insured	x (xx)				
Geographic Rural Urban / Suburban	x (xx)				

CENEOCCODY INC	Title: CRC-PREVENT Clinical Validation Protocol
GENEOSCOPY, INC.	Document Number: VAL-PRT-0041

TO III 4 D		C 11	1	111 1	. 1	•	C . 1.1
Table 4 Data	summaries 1	tor all	subjects	Will be	siimmarized	1n a	frequency table:

Mt-sRNA Test	His	Histopathological Lesion Category Grouping				
Result	CRC	AA	OA	Negative	Total	
Positive	a	ь	С	d	a+b+c+d	
Negative	e	f	g	h	e+f+g+h	
Total	a+e	b+f	c+g	d+h	N	

The primary endpoint metrics will be calculated as:

- mt-sRNA test sensitivity for subjects with CRC = a / (a+e)
- mt-sRNA test sensitivity for subjects with AA = b / (b+f)
- mt-sRNA test specificity for subjects with negative findings = h/(d+f)

For each of these metrics, the two-sided 95% exact binomial confidence intervals will be provided, and the lower 95% confidence limits will be compared to the acceptance criterion. An additional sensitivity calculation will be presented for subjects with Other Adenomas.

• mt-sRNA test sensitivity for subjects with OA = c/(c+g)

The two-sided 95% confidence interval will be calculated for this metric although there is no specific acceptance criterion against which it will be compared.

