#### 4.2.1 Primary Study Endpoints

The primary objective of this study will be assessed using four co-primary performance measures or study endpoints:

• mt-sRNA test sensitivity for subjects with colorectal cancer (CRC), which is the percentage of individuals with a diagnosis of colorectal cancer (**Table 1**) that were detected as positive by the mt-sRNA test.

	Title: CRC-PREVENT Statistical Analysis Plan
GENEOSCOPY, INC.	Document Number: CT-PLN-0002

- mt-sRNA test sensitivity for subjects with advanced adenomas (AA), which is the percentage of individuals with a diagnosis of advanced adenoma (**Table 1**) that were detected as positive by the mt-sRNA test.
- mt-sRNA test specificity for subjects with negative findings, which is the percentage of individuals with a diagnosis of benign polyps, or no findings on a colonoscopy (**Table 1**) that were detected as negative by the mt-sRNA test.

Criteria for success for these metrics requires the following:

- With regards to the mt-sRNA test sensitivity for subjects with CRC, the sensitivity of CRC must be greater than 90% and the lower bound of the 95% two-sided confidence interval must be greater than 80%.
- With regards to the mt-sRNA test sensitivity for subjects with AA, the sensitivity of AA must be greater than 45% and the lower bound of the 95% two-sided confidence interval must be greater than 40%.
- With regards to the mt-sRNA test specificity for subjects with no findings on a colonoscopy, the specificity must be greater than 80%.

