## 6. Sample Size

The overall sample size for the study is driven by the need to obtain enough CRC cases so that the lower 95% exact confidence limit for the sensitivity is at least 80%. **Table 3** shows the smallest number of CRC cases that would meet this condition for each of 0 - 5 False Negatives.

Table 3. CRC cases required to meet primary objective criteria

Number of CRC Cases	# False Negative	Observed Sensitivity	Lower 95% CL	Upper 95% CL
17	0	100.0%	80.5%	100.0%
26	1	96.2%	80.4%	99.9%

	Title: CRC-PREVENT Statistical Analysis Plan						
GENEOSCOPY, INC.	Document Number: CT-PLN-0002						
34	2	94.1%	80.3%	99.3%			
41	3	92.7%	80.1%	98.5%			
48	4	91.7%	80.0%	97.7%			
55	5	90.9%	80.0%	97.0%			

A sample size of 48 would allow up to 4 false negatives corresponding to an observed sensitivity of 91.7%. Assuming a prevalence of 0.6% in the intended use population, a starting sample size of 8,500 will have a 68% chance of yielding at least 48 CRC cases. Given the low prevalence of CRC cases, a small difference between the actual prevalence and the postulated prevalence could lead to too few CRC cases.

The number of CRC cases will be tracked by non-clinical study members at Geneoscopy's selected CRO during pathology review of colonoscopy reports. Enrollment will be arrested when a sufficient number of confirmed cases of CRC have been identified among the cohort to achieve study endpoints.

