**Document Number: CT-PLN-0002** 

| Insurance No Insurance Private Insurance Public Insurance (Medicaid) Public Insurance (Medicare Advantage) Public Insurance (Medicare) Self-Insured | x (xx) |
|---|--------|--------|--------|--------|--------|--------|
| Geographic
Rural
Urban / Suburban   | x (xx) |

Table 6. Data summaries for subject categories will be generated for sensitivity and specificity

Category	Label	True Outcome	Colonoscopy Findings	% (N)
1	Colorectal Cancer	Positive	Stage I-IV colorectal cancer, any size	x (xx)
2	Advanced adenoma	Positive	High-grade dysplasia or ≥10 adenomas, any size Tubulovillous adenoma, any size Tubular adenoma, ≥10mm Traditional serrated adenoma, any size	x (xx)
3	Other adenoma	Negative	Hyperplastic polyp or SSL, ≥10mm 5-9 adenomas (TA + SSL), <10mm 3-4 adenomas (TA + SSL), <10mm	x (xx)
4	Other adenoma	Negative	1-2 adenomas (TA + SSL), 5-9mm 1-2 adenomas (TA + SSL), <5mm	x (xx)
5	Negative	Negative	Hyperplastic polyps, <10mm Benign lesions, any size No lesions on colonoscopy	x (xx)

**Table 7.** Data summaries for all subjects will be summarized in a frequency table:

	Ti
GENEOSCOPY, INC.	D

**Fitle:** CRC-PREVENT Statistical Analysis Plan

**Document Number:** CT-PLN-0002

Mt-sRNA Test Result		Histopathological Lesion Category Grouping						
	CRC (1) % (n)	AA (2) % (n)	OA (3) % (n)	OA (4) % (n)	NEG (5) % (n)	Total		
Positive	a	b	С	d	e	a+b+c+d+e		
Negative	f	g	h	i	j	f+g+h+i+j		
Total	a+f	b+g	c+h	d+i	e+j	N		

The primary endpoint metrics will be calculated as:

- Mt-sRNA test sensitivity for subjects with CRC = a / (a+f)
- Mt-sRNA test sensitivity for subjects with AA = b / (b+g)
- Mt-sRNA test specificity for subjects with negative findings = j / (e+j)

For each of these metrics, the two-sided 95% exact binomial confidence intervals will be provided, and the lower 95% confidence limits will be compared to the acceptance criterion. An additional sensitivity calculation will be presented for subjects with Other Adenomas.

- Mt-sRNA test sensitivity for subjects with OA(3) = c/(c+h)
- Mt-sRNA test sensitivity for subjects with OA(4) = d/(d+i)

The two-sided 95% confidence interval will be calculated for this metric although there is no specific acceptance criterion against which it will be compared.

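### The joint hypothesis in protocol 2.1 contradicts itself on CRC and tests values other than those behind the confidence-limit criteria; separately, the specificity pass rule has two readings

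*Protocol*

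**What the plan says.** **Success criteria.** Protocol 2.1 and SAP 4.2.1 give the same list. The cancer criterion reads: "the sensitivity of CRC must be greater than 90% and the lower bound of the 95% two-sided confidence interval must be greater than 80"%. AA has the same two-part form, with 45% for the estimate and 40% for the limit. Specificity has one part: "With regards to the mt-sRNA test specificity for subjects with no findings on a colonoscopy, the specificity must be greater than 80"%.

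**Hypothesis.** Protocol 2.1 then recasts these as a joint hypothesis. H0 is CRC sensitivity at most 0.90, or AA sensitivity at most 0.45, or specificity at most 0.80. H1 is "CRC_{Sen} > 0.65 and AA_{Sen} > 0.45 and Sp > 0.80". It adds: "The associated p-values for two-sided 0.05 exact binomial tests will also be provided". The SAP contains neither the hypothesis nor these p-values.

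**Sample size.** Protocol 3.5 (Sample Size Requirements) gives this basis for the number enrolled: "driven by the need to obtain enough CRC cases so that the lower 95% exact confidence limit for the sensitivity is at least 80"%. SAP section 6 uses the same basis.

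**Analysis rule.** Protocol 3.5 (Primary Statistical Analysis Plan) lists CRC sensitivity, AA sensitivity and specificity as the primary metrics and continues: "For each of these metrics, the two-sided 95% exact binomial confidence intervals will be provided, and the lower 95% confidence limits will be compared" with the criterion. SAP 9.1 lists the same three and also says that "the lower 95% confidence limits will be compared to the acceptance criterion".

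**The concern.** Two separate things need reconciling.

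*The tested values.* A null and its alternative should not both hold for the same truth. Here any CRC sensitivity above 0.65 and up to 0.90, with AA above 0.45 and specificity above 0.80, satisfies both. Changing 0.65 to 0.90 would remove the overlap but leave a second mismatch: 0.90 and 0.45 are hurdles for the observed estimate, while the confidence limits test 0.80 and 0.40. If the protocol sentence on p-values is followed, a successful CRC result would be reported beside a p-value far from significance for the trial's own stated null, in a study whose objectives are meant to support regulatory claims.

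*The specificity rule.* An observed specificity a little above 80% passes if only the estimate counts and fails if the lower limit counts. Settling this after the results are known would be a data-dependent choice.

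**Working it through.** **1. The plan's own figures reproduce.** Inputs are the rows of protocol Table 2 (SAP Table 3). The Clopper-Pearson lower limit for x positives of n is the 2.5% quantile of Beta(x, n - x + 1). The one-sided p-value against p0 is P(X >= x) for X ~ Binomial(n, p0).

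| Positives/cases | Lower limit | One-sided p vs 0.80 | One-sided p vs 0.90 |
|---|---|---|---|
| 17/17 | 80.49% | 0.0225 | 0.167 |
| 25/26 | 80.36% | 0.0227 | 0.251 |
| 32/34 | 80.32% | 0.0226 | 0.326 |
| 38/41 | 80.08% | 0.0244 | 0.403 |
| 44/48 | 80.02% | 0.0248 | 0.469 |
| 50/55 | 80.05% | 0.0245 | 0.524 |

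Each n is the smallest that clears 80% for its number of false negatives. P(X >= 48) for Binomial(8500, 0.006) is 0.682, against the stated 68%. The case count is therefore sound, and it is built on 0.80.

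**2. The printed CRC null.** Every row clears the 80% limit and has an estimate above 90%; none rejects 0.90. For 44/48 the two-sided p-value against 0.90 is 0.94 (doubled tail) or 1.0 (minimum likelihood).

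**3. The AA null.** The documents give no AA case count. Assume the feasibility hold-out mix in protocol 1.2 applied to 8,500: 50/366 x 8,500 = 1,161. The smallest passing result is 523/1161 = 45.05%, with lower limit 42.2%. Its one-sided p is 0.50 against 0.45 and 0.0003 against 0.40.

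**4. The reverse mismatch.** With nulls of 0.80 and 0.40, a significant p-value can sit beside a failure, because with many cases the point estimate is the binding part:

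- AA 522/1161 = 44.96%: doubled p = 2 x 0.00033 = 0.0007 against 0.40, but fails the 45% hurdle.
- CRC 63/70 = 90.0%: lower limit 80.5%, doubled p = 0.040 against 0.80, but is not above 90%.

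**5. Which two-sided p-value.** Against 0.80, the doubled tail gives 0.045 to 0.050 over the six rows, all below 0.05, as the limits require. Minimum likelihood can disagree in both directions: 32/34 gives p = 0.05004 with a limit above 80%, and 43/47 gives p = 0.046 with a limit of 79.6% (doubled tail 0.057).

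**6. Specificity.** The number of subjects in the No Findings (NEG) category is not given. Assume 2,000, 4,064 (175/366 x 8,500) or 8,000. The gap is an observed value above 80% whose lower limit is not above 80%.

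| Negatives | Smallest count with limit above 80% | Pass chance at true 80%: estimate / limit | Chance of gap at true 81% | at 82% | at 82.9% |
|---|---|---|---|---|---|
| 2,000 | 1636 (81.8%) | 49.1% / 2.3% | 68% | 38% | 9% |
| 4,064 | 3302 (81.25%) | 49.7% / 2.4% | 60% | 10% | 0.3% |
| 8,000 | 6471 (80.9%) | 49.6% / 2.4% | 38% | 0.5% | below 0.1% |

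The 82.9% scenario is (0.85 x 101 + 0.80 x 74)/175, from the no-findings and hyperplastic-polyp figures in protocol 1.2. That section labels both as sensitivity; they are read here as percent test-negative.

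**The case against.** The strongest reply is that the hypothesis changes no decision. The CRC and AA rules are explicit and identical in both documents, the p-values are only an addition, and the SAP, which governs the analysis, omits both. That stands: this part is a correction of a stated test, not of the success rule. A reader might infer that the CRC case count or the CRC claim is undermined; the reproduced table shows otherwise.

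A second reply is that moving the nulls to 0.80 and 0.40 only reverses the mismatch (step 4), and lowers the written nulls after enrolment closed (SAP 7.1). Both are true and must be disclosed. They are reasons to state that a p-value alone is not success, or to drop the line altogether; they do not justify leaving the overlap in place.

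On specificity, a reader might infer that nothing in the documents fixes the rule. That goes too far. The success lists attach a limit to CRC and AA and none to specificity, in both documents, and specific text normally outranks a generic sentence. This favours the point-estimate reading. It does not settle it, because both analysis sections apply the limit to each listed metric and protocol 2.1 itself tests specificity against 0.80.

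Finally, the specificity inputs are weak. It is tempting to call 82.9% the feasibility value for the NEG category, but protocol 1.2 gives hyperplastic polyps without a size limit, whereas NEG in Table 1 takes only those under 10 mm. It serves here only as a scenario. The scaled counts also use 8,500 recruited rather than evaluable subjects, and SAP 7.1 reports about 14,000 consented.

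**Conclusion.** The point holds and should be fixed. The CRC hypothesis is contradictory as printed, and its null does not match the 0.80 on which the confidence limit and the case count rest; the AA null likewise differs from the 0.40 its limit tests. The consequence is in reporting: 44/48 succeeds, yet has one-sided p = 0.47 against the printed null. The CRC and AA success decisions are unaffected.

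The specificity conflict is the only part that can change an outcome. The readings differ for observed values from just above 80% up to about 81.8% (2,000 negatives), 81.25% (4,064) or 80.9% (8,000). If true specificity is about 83% or more, the chance of landing there is 0.3% or less with 4,000 or more negatives, and about 9% with 2,000. At a true 80%, the rules pass about 49-50% and 2.4% of the time. These figures depend on the assumed numbers of negatives; the CRC figures need no outside assumption.

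**What to change.** Make the change in a version dated before the two locked datasets are merged.

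- **Hypothesis, option A.** Delete 0.65. State the tested nulls as CRC at most 0.80 and AA at most 0.40, with H1 the exact complement. Keep the 90% and 45% hurdles as separate point-estimate requirements. Say that success needs both parts and that a significant p-value alone is not success. Record that the written nulls were lowered after enrolment closed and that the success criteria were not changed.
- **Hypothesis, option B.** Delete the joint-hypothesis line and its p-values and rely on the explicit success rule, as the SAP does.
- **P-values, if kept.** Use the doubled one-sided tail, so that they agree with the Clopper-Pearson limits, and say in the SAP that they will be reported.
- **Specificity.** State one rule in protocol 2.1, protocol 3.5 (Primary Statistical Analysis Plan), SAP 4.2.1 and SAP 9.1. Either require a lower 95% limit above 80%, or use the point estimate only, take specificity out of H0, exempt it from the lower-limit sentence and describe it as not formally tested.

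**Cost.** Wording only: no extra participants and no change to the CRC or AA decisions. The lower-limit option raises the observed specificity hurdle by about 0.9 points (8,000 negatives) to 1.8 points (2,000). The point-estimate option leaves the hurdle where it is but gives up an error-controlled specificity claim.
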